Title: High Dose Omega-3 Fatty Acids in the Treatment of Sport Related Concussions

NCT: 01814527

Completion Date: 4/25/2018

Methods

This study obtained IRB approval prior to enrollment of participants through East Carolina University and Medical Institutional Review Board. The study design was a randomized double-blind placebo-controlled trial using student's T test for analysis of continuous outcome variables. This study was conducted at East Carolina University over a 4 year period. The inclusion criteria for each subject were: must be a NCAA Division I student athlete at East Carolina University, must be 18 years old, have sustained a sport related concussion within the past 24 hours, and have a neurological exam not consistent with concern for an intracranial hemorrhage or other significant pathology. The exclusion criteria for each participant was: a recent prior concussion within the past 30 days, a history of moderate to severe TBI that has required hospitalization or resulted in prolonged signs and/or symptoms (>3 weeks), a known neurological diagnosis associated with impaired cognitive function other than attention deficit hyperactivity disorder or attention deficit disorder, a known allergy to algae, omega-3 fatty acid, or any component of the formulation, a known liver pathology or significantly elevated LFTs (greater than 3 x normal), a current lower extremity injury that will affect postural stability testing, subjects already routinely using omega-3/DHA supplementation, and subjects currently requiring anticoagulants, anti-platelets or any NSAIDs.

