Once a student-athlete was diagnosed with a sport related concussion, and met the inclusion and exclusion criteria, the athlete met with the primary investigator and an IRB approved informed consent was obtained. The athlete then was randomly assigned to either high dose omega-3 fatty acid/DHA supplementation or placebo. Demographics of the athlete were obtained and include age, gender, sport, academic year, height, weight, BMI, history of prior concussion, migraines, learning disability, or psychiatric diagnosis. The experimental group was given a standardized dose of 2 grams (4 capsules) of omega-3 fatty acid/DHA for 30 days after onset of concussion. The placebo group was given an equal number of capsules. Both the omega-3 fatty acid/DHA capsules and placebo capsules were donated to East Carolina University for the purpose of this study by DSM Nutritional Products. The omega-3 fatty acid/DHA used in this study was derived from algae and therefore had no fish odor or after taste. The physician and the athletic training staff evaluating and clearing the athlete to return to activity were blinded. Each athlete underwent daily directly observed therapy by certified athletic trainers and daily symptom monitoring using the Symptom Evaluation scale found on the Sport Concussion Assessment Tool 2 (SCAT2). Symptoms were grouped into physical, cognitive, emotional and sleep categories with the total number of symptoms and symptoms severity score calculated for each category and overall.

Both groups underwent standard and usual care for concussed athletes at East Carolina University. East Carolina University employs a regimented return-to-play protocol for every student-athlete that has sustained a concussion (Figure 1). As part of their pre-participation physical, all student-athletes have a baseline computerized neuro-physical postural stability test using Bidex SD/BioSway and a computerized neurocognitive test using ImPact. At the time of

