injury, a SCAT2 is administered by a certified athletic trainer, and the student-athlete is withdrawn from participation if they are symptomatic and/or have deficits noted. The same day a concussion is suspected a repeat Bidex postural stability test is administered and the student-athlete is given a detailed information sheet on instructions for monitoring and follow-up. A repeat Impact neurocognitive test is administered within 24 hours after the injury. The student-athlete is then seen and examined by a sports medicine physician to review the results, perform a clinical examination, and confirm the diagnosis. The student-athlete is then evaluated daily with a modified Symptom Evaluation Questionnaire found on the SCAT2 by an athletic trainer. When the student-athlete is asymptomatic with activities of daily living (ADLs) for 24 hours, he/she then begins a non-contact return to play protocol beginning with a supervised cardiovascular challenge. This includes 30 minutes of supervised light aerobic activity on a treadmill or stationary bike. If the athlete is asymptomatic with the cardiovascular challenge, then he/she can progress to noncontact sport specific drills the subsequent day. If the athlete is still doing well, he/she can progress their non-contact training drills and start light resistance training the following day. If the student-athlete remains asymptomatic through the non-contact activity progression, he/she then re-takes the computerized neurocognitive test, postural stability assessment and is re-evaluated by the physician. If the postural stability assessment and neurocognitive test are back to baseline the athlete is then cleared at the discretion of the treating sports medicine physician to return to full unrestricted activity. However, if a student-athlete continues to be symptomatic on day 7 both Impact and Bidex SD/BioSway evaluation will be re-administered. This will be repeated at 14 days and 30 days post-injury if the student-athlete continues to be symptomatic (Figure 1). The primary outcome of the study is the total number of days from onset of concussion it takes for the athlete to return to unrestricted full participation in their respective sport.

Results

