A total of 62 student-athletes were enrolled and completed the study. 7 student-athletes were excluded from the analysis secondary to return to play greater than 30 days. Of those 7 student-athletes 6 were in the DHA cohort and 1 was in the placebo cohort. 55 student-athletes (33 male and 22 female) were used in the analysis. The demographics of the DHA cohort were: 19.7 ± 1.4 years of old, 60.9% male, 39.1% female, and a BMI of 27.7 ± 6.1 . The demographics of the placebo cohort were: 19.9 ± 1.4 years of age, 59.4% male, 40.6% female, and a BMI of 28.3 ± 6.1 . There was no statistically significant difference in age, gender, BMI, and sports distribution in the DHA vs the placebo cohort. Direct observed therapy of the intervention lead to a compliance rate of 84.2% in the DHA cohort and 83.0% in the placebo cohort. A previous history of concussion prior to the study was recorded and there was no statistical difference between the cohorts with the DHA cohort at 47.8% and the placebo cohort at 50%. The initial SCAT2 symptom severity score, an indicator of concussion severity, was recorded. The DHA cohort's initial SCAT2 symptom severity score was 42.7 ± 27.9 compared to the placebo cohort's initial SCAT2 symptom severity score of 49.9 ± 26.6 . Despite the placebo cohort's higher symptom

severity score this was not statistically significant. The primary outcome of this study was the number of days that the athlete required to return to play. The DHA cohort's return to play was 11.0 ± 4.8 days [95% CI 9.1,13.0] and the placebo cohort's return to play was 11.9 ± 5.4 days [95% CI 10.0,13.8], with a P value of 0.558 (Figure 2). The effect size was calculated to be 0.16 and a post hoc power analysis was calculated to be 0.09.

Figure 1: East Carolina University Concussion Management Standardized Protocol

[figure not shown]

Figure 2: Results

	DHA (n= 23)	Placebo (n=32)
Age (years)	19.7 ± 1.4	19.9 ± 1.4
Gender (male: female)	60.9%: 39.1%	59.4%: 40.6%
BMI (kg/m ²)	27.7 ± 6.1	28.3 ± 6.1
Compliance	84.20%	83.02%
History of Concussion	47.8%	50%
SCAT2 Symptom Severity Score	42.7 ± 27.9	49.9 ± 26.6
Return to Play (days) (P=0.558)	11.0 ± 4.8 [95% CI 9.1,13.0]	11.9 ± 5.4 [95% CI 10.0,13.8]

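### The primary comparison omits seven completers because they returned after day 30 (6 DHA, 1 placebo) and has no between-arm confidence interval; on all 62 the 30-day restricted mean changes direction

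*Combined protocol and SAP*

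**What the plan says.** Methods defines the primary outcome as "the total number of days from onset of concussion it takes for the athlete to return to unrestricted full participation" in the athlete's sport, and the design paragraph describes the trial as "using student's T test for analysis of continuous outcome variables".

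Methods uses a 30-day figure in three places, none of which limits the outcome or the analysis set:
- the exclusion criterion on "a recent prior concussion within the past 30 days";
- the capsule period, "for 30 days after onset of concussion";
- the retesting schedule, "This will be repeated at 14 days and 30 days post-injury if the student-athlete continues to be symptomatic".

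Results opens with "A total of 62 student-athletes were enrolled and completed the study" and continues: "7 student-athletes were excluded from the analysis secondary to return to play greater than 30 days". Six of the seven were on DHA and one was on placebo, which leaves 23 and 32.

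For those 55, Results and Figure 2 give each arm's mean, SD and 95% CI (DHA 11.0 ± 4.8, 9.1 to 13.0; placebo 11.9 ± 5.4, 10.0 to 13.8) and P=0.558. Results adds an effect size of 0.16 and states that "a post hoc power analysis was calculated to be 0.09". Neither place gives a difference between arms or an interval for one.

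**The concern.** The seven athletes finished the study and have a primary outcome; they were left out because that outcome was long. An analysis limited to those back by day 30 compares arms after selection on the result, and the selection fell unevenly: 20.7% of DHA completers against 3.0% of placebo completers. Removing the slowest athletes mainly from one arm shortens that arm's mean.

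The t test compares the arms, so the quantity to report is the difference in days with its interval. Two single-arm intervals do not supply it. Without it the reader cannot see which benefits or delays the data allow, and on the 55 alone the answer would still describe only athletes who recovered within 30 days.

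The post hoc power is a lesser matter. It is the only power figure given, and it says nothing about sensitivity to a worthwhile difference.

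**Working it through.** **Inputs (Results and Figure 2).** DHA n=23, mean 11.0, SD 4.8; placebo n=32, mean 11.9, SD 5.4; P=0.558; removed 6 and 1. Completers are therefore 23+6=29 and 32+1=33. No significance level is stated; two-sided 0.05 is assumed. Differences are DHA minus placebo.

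**1. The printed effect size and power.** From P=0.558 with 53 df, |t|=0.5895. Then d = 0.5895 × √(1/23+1/32) = 0.161, and noncentral-t power at that d is 0.089. Both printed figures (0.16 and 0.09) follow from P and the arm sizes.

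**2. The printed intervals are single-arm.** Placebo: 11.9 ± 1.96 × 5.4/√32 = 10.0 to 13.8. DHA: 11.0 ± 1.96 × 4.8/√23 = 9.0 to 13.0, against 9.1 to 13.0 printed.

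**3. Difference on the 55.** Pooled SD = √[(22×4.8² + 31×5.4²)/53] = 5.16; SE = 5.16 × √(1/23+1/32) = 1.410. Difference 11.0 − 11.9 = −0.9, 95% CI −3.73 to +1.93. Welch: SE 1.383, df 50.5, −3.68 to +1.88. The rounded means imply P=0.526, and rounding of the inputs allows 0.477 to 0.577, so 0.558 is compatible. Working back from P=0.558 gives −0.83 (−3.66 to +2.00).

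**4. 30-day restricted mean on all 62.** Each athlete contributes days to return or 30, whichever is smaller. The seven contribute exactly 30. The 55 contribute their own days, taken as at most 30, as the exclusion rule implies; for them the restricted mean equals the ordinary mean, so steps 3 and 4 are on the same scale.

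| | DHA | Placebo |
|---|---|---|
| Mean | (23×11.0 + 6×30)/29 = 14.93 | (32×11.9 + 1×30)/33 = 12.45 |
| Sum of squares | 22×4.8² + 23×(11.0−14.93)² + 6×(30−14.93)² | 31×5.4² + 32×(11.9−12.45)² + (30−12.45)² |
| SD (divide by n−1, take root) | 8.91 | 6.18 |

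Difference +2.48. Welch SE = √(8.91²/29 + 6.18²/33) = 1.974, df 49.0, 95% CI −1.48 to +6.45, P=0.21. Pooled: SE 1.929, −1.38 to +6.34.

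Check: restoring the seven raises the DHA mean by 6×(30−11.0)/29 = 3.93 and the placebo mean by (30−11.9)/33 = 0.55; −0.9 + 3.93 − 0.55 = +2.48.

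Moving every printed mean and SD by ±0.05 keeps the estimate between +2.39 and +2.57, the lower Welch limit between −1.59 and −1.38, and the upper between +6.35 and +6.55.

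**5. Untruncated days on all 62 (illustration only).** The late days are not given. One common assumed value for all seven gives:

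| Assumed day | Difference | Welch 95% CI |
|---|---|---|
| 31 | +2.7 | −1.4 to +6.8 |
| 45 | +5.1 | −1.0 to +11.3 |
| 60 | +7.8 | −0.7 to +16.3 |

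These are not bounds, because a later placebo return lowers the difference. With the six DHA athletes at day 31, the DHA mean is (253+186)/29 = 15.14. The placebo mean equals it when the one late placebo day is 33×15.138 − 380.8 = 118.8, so a placebo return after about day 119 would reverse the sign.

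**The case against.** **The missing interval and the 0.09 are minor reporting points.** This stands. A reader can derive the interval on the 55, Results draws no conclusion from the 0.09, and correcting either alone would change almost nothing. The weight lies in which athletes the comparison covers.

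**The inference does not change.** True as far as significance goes: neither interval excludes zero. But the largest benefit compatible with the data falls from 3.7 to 1.5 days and the largest delay rises from 1.9 to 6.4, which is a different reading of the trial.

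**The direction on all 62 rests on values nobody outside the trial has seen.** This stands for untruncated days. It does not touch the restricted mean, where each late athlete's contribution is known.

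**A raw-day comparison is fragile, and other methods are defensible.** Also fair. A few values in an unknown right tail can move a mean, which is why the restricted mean should be reported in any case. A time-to-return analysis that keeps all 62 is another reasonable choice; the documents do not settle which is best.

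**Stronger readings.** A reader might infer from 6/29 against 1/33 (Fisher P about 0.04) that DHA delays recovery. The documents do not support that: the contrast is picked out by the exclusion itself, rests on seven athletes, and the all-62 interval in days includes zero. A reader might also infer that the cut-off was chosen to favour DHA. The documents do not say when or why it was set; they show only that Methods does not contain it.

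**Conclusion.** The concern holds. Seven of 62 completers were removed on the value of the primary outcome, unevenly by arm, although the outcome as defined has no 30-day limit, and no between-arm difference or interval is reported on any set. On the 30-day restricted mean the estimate goes from −0.9 days on the 55 to about +2.5 days on all 62, DHA slower. That is a changed direction, not proven harm.

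The result assumes that the 55 were all back by day 30, that the 29/33 split follows from the printed counts, and that t-based intervals are adequate for data with a cluster at day 30. It needs no assumed late days. For untruncated days the same direction is likely, but the documents do not fix it. The post hoc power of 0.09 adds nothing to P=0.558.

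**What to change.** Report the DHA-minus-placebo difference with its 95% CI on all 62 athletes:
- as the 30-day restricted mean time to return, using Welch because the arm SDs become unequal (8.91 and 6.18);
- also on the recorded return days, if they are held.

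Interpret the trial from that all-62 interval. If the analysis of the 55 is kept, label it as limited to athletes back by day 30 and give its difference and interval too. State when and why the 30-day exclusion was adopted. Drop the post hoc power.

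The cost is a small reanalysis of data already collected, with no new participants, and a less favourable estimate for DHA: about +2.5 days on the restricted mean in place of −0.9.
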